10.5. Data Safety Monitoring Board

An independent DSMB will be established to perform ongoing safety surveillance. The voting members on the DSMB are external to the Sponsor and are not involved with the trial in any other way and have no competing interests that could affect their roles with respect to the trial.

During the conduct of the study, the safety data of the study will be collected on an ongoing basis and provided to the DSMB. The DSMB will monitor the general safety and the endometrial safety of the trial at an appropriate frequency as provided in the DSMB charter and will make recommendations to the Sponsor regarding steps to ensure the safety of the trial subjects. The DSMB will be supported by a Clinical Event Committee who will adjudicate cardiovascular and thrombotic events in a consistent and unbiased manner throughout the course of the study.

More details on the DSMB, including the composition, responsibilities, timing and organization of the meetings and administrative structure will be described in a separate DSMB charter.

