## **3 STUDY DESIGN**

### **3.1 General Study Design**

This study is a Phase III study, with multiple centers in the USA and Canada. Eligible subjects will be post-menopausal women,  $\geq 40$  up to  $\leq 65$  years of age, seeking treatment for relief of moderate to severe vasomotor symptoms (VMS) associated with menopause.

The Safety Study part will be conducted in approximately 200 hysterectomized and approximately 200 non-hysterectomized postmenopausal women, who are seeking treatment for the relief of VMS (condition clinically indicated by the investigator) associated with menopause and have at least 1 moderate to severe VMS symptom per week.

The Safety Study part is an open label study, to evaluate the effect of E4 20 mg (Arm 4) on the primary safety and secondary efficacy endpoints (lipid and glucose metabolism, HRQoL and TS) over a 52 week treatment period. For endometrial protection, all non-hysterectomized subjects will receive treatment with 200 mg progesterone (P4) once daily for 14 consecutive days, after completion of the E4 treatment. The target number of subjects to be included in the Safety Study part is approximately 400. Enrollment in the Safety Study part will stop as soon as the minimum required number of subjects in each study group and study part is enrolled.

[figure not shown]
At least 8 visits (up to 15 months) are planned in the Safety Study part, this includes:

- Washout visit (occurring generally up to 8 weeks prior to Screening visit),
- Screening visit (occurring 4 weeks prior to Baseline [Visit 1]),
- Treatment visits (occurring within 53 weeks; Visit 1 to Visit 6), include:
  - Baseline (Visit 1),
  - Five On-treatment visits (Visits 2, 3, 4, 5 and 6), the last treatment visit (Visit 6) is also the end of treatment (EoT) visit, which will also occur in case of early discontinuation.

For non-hysterectomized women an additional endometrial safety follow-up visit (visit 7) is planned approximately 10 days after completion of the 14 days of P4 treatment, which will also occur in case of early discontinuation

The trial schedule for Safety Study part is summarized in [Figure 1](#).

Figure 1: Trial Schedule

EoT = End of Treatment; NH = Non-hysterectomized; H = Hysterectomized; E4 = estetrol; P4 = progesterone

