**Table 1: Derived Variables**

Variables	Formula																								
Demographic and Baseline Characteristics																									
Body mass index (BMI) (kg/m  )	weight (kg)/[height (m)] 																								
Study Treatment																									
Treatment Start Date	The date of first dose of study drug.																								
Treatment Stop Date	The date of last dose of study drug.																								
Duration of exposure (Days)	(Treatment Stop Date – Treatment Start Date) + 1																								
Treatment compliance (%)	100 x [(total number of tablets dispensed) – (total number of tablets returned)]/(duration of exposure in days)																								
Study Day	Prior to Treatment Start Date: Date of interest – Treatment Start Date  On or after Treatment Start Date: Date of interest – Treatment Start Date + 1																								
Study Week	
Study Week is defined as follows for the first 7 weeks
 
  
 Week	Start (Study Day)	End (Study Day)	
   
 1	1	7	
 
 2	8	14	
 
 3	15	21	
 
 4	22	28	
 
 5	29	35	
 
 6	36	42	
 
 7	43	49	
  
	Week	Start (Study Day)	End (Study Day)	1	1	7	2	8	14	3	15	21	4	22	28	5	29	35	6	36	42	7	43	49
Week	Start (Study Day)	End (Study Day)																							
1	1	7																							
2	8	14																							
3	15	21																							
4	22	28																							
5	29	35																							
6	36	42																							
7	43	49																							

Study Cycle	28-day period starting from Treatment Start Day
Adverse Events	
Adverse Event (AE) Start Day	Prior to Treatment Start Date: AE start date – Treatment Start Date  On or after Treatment Start Date: AE Start Date – Treatment Start Date + 1
AE Stop Day	Prior to Treatment Start Date: AE stop date – Treatment Start Date  On or after Treatment Start Date: AE stop date – Treatment Start Date + 1
AE Duration (Days)	(AE Stop Date – AE Start Date) + 1

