TEAE	AE Start Date known: TEAE if AE Start Date on or after Treatment Start Date and AE Start Date is before the date of the last visit where last visit is defined as end of treatment, early discontinuation or follow up visit (for NH subjects).  AE Start Date unknown: TEAE if AE Stop Date is on or after Treatment Start Date.
Baseline	
Baseline	Unless otherwise noted, Baseline is defined as the last non-missing value, including results from repeated and unscheduled measurements, prior to Treatment Start Date.
Change from Baseline	Date of interest – Baseline
Other	
TS	TS is the percentage of subjects in each category in CGI questionnaire (very much improved, much improved, minimally improved, no change, minimally worse, much worse, and very much worse) which will be presented at week 4, week 12 and week 52 for the different treatment group.

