Collecting and recording AESIs will begin on Treatment Start Date and will end at the follow-up visit. AESI collection will start at each site from the date of the Ministry of Health and/or Institutional Review Board (IRB)/Ethics Committee (EC) approval date of Protocol Version 6.0 (Amendment 5). There will not be any retrospective reporting.

An overview of TEAEs will be presented for the Safety Analysis Set with the frequency counts and percentages of subjects with at least one:

- TEAE;
- Severe TEAEs;
- Drug related TEAEs;

- Serious TEAE;
- Drug related serious TEAEs;
- TEAEs leading to dose interruption;
- TEAEs leading to study drug discontinuation;
- TEAEs leading to death;
- Drug related TEAEs leading to death;
- AESI

The overview table will also be presented by hysterectomy status (hysterectomized and non-hysterectomized).

All TEAEs (including AESI and SAE), SAE (including serious AESI) and AESI (including both serious and non-serious AESI) will also be summarized for the Safety Analysis Set as below:

- TEAEs by SOC, PT;
- TEAEs of reproductive system and abdominal pain by SOC, PT by hysterectomy status (hysterectomized and non- hysterectomized), as defined in [Table 4](#);
- TEAEs by SOC, PT and maximum intensity;
- TEAEs of reproductive system and abdominal pain by SOC, PT and maximum intensity by hysterectomy status (hysterectomized and non- hysterectomized), as defined in [Table 4](#);
- Drug related TEAEs by SOC, PT and maximum intensity;
- Drug related TEAEs of reproductive system and abdominal pain by SOC, PT and maximum intensity by hysterectomy status (hysterectomized and non- hysterectomized), as defined in [Table 4](#);
- TEAEs leading to study drug interruption by SOC, PT, and maximum intensity;
- TEAEs of reproductive system and abdominal pain that leading to study drug interruption by SOC, PT and maximum intensity by hysterectomy status (hysterectomized and non-hysterectomized), as defined in [Table 4](#);
- TEAEs leading to study drug discontinuation by SOC, PT, and maximum intensity;
- TEAEs of reproductive system and abdominal pain that leading to study drug discontinuation by SOC, PT and maximum intensity by hysterectomy status (hysterectomized and non- hysterectomized) ), as defined in [Table 4](#);
- Serious TEAEs by SOC, PT;
- Serious TEAEs of reproductive system and abdominal pain by SOC, PT by hysterectomy status (hysterectomized and non- hysterectomized), as defined in [Table 4](#);

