- Serious TEAEs by SOC, PT and maximum intensity;
- Serious TEAEs of reproductive system and abdominal pain by SOC, PT and maximum intensity by hysterectomy status (hysterectomized and non- hysterectomized), as defined in [Table 4](#);
- Drug related serious TEAEs by SOC, PT and maximum intensity;
- Drug related serious TEAEs of reproductive system and abdominal pain by SOC, PT and maximum intensity by hysterectomy status (hysterectomized and non- hysterectomized), as defined in [Table 4](#);

- TEAEs leading to deaths, by SOC, PT and maximum intensity;
- TEAEs of reproductive system and abdominal pain that leading to deaths, by SOC, PT and maximum intensity by hysterectomy status (hysterectomized and non- hysterectomized), as defined in [Table 4](#);
- Drug related TEAEs leading to deaths, by SOC, PT and maximum intensity;
- Drug related TEAEs of reproductive system and abdominal pain that leading to deaths, by SOC, PT and maximum intensity by hysterectomy status (hysterectomized and non-hysterectomized), as defined in [Table 4](#);
- AESI by SOC, PT and hysterectomy status (hysterectomized and non- hysterectomized);
- AESI by SOC, PT and maximum intensity and hysterectomy status (hysterectomized and non-hysterectomized);
- Venous thromboembolism events (VTE) incidence and cardiovascular events incidence, with additional information as defined below:

Number of Subjects with at least one event in each of the following categories:

- VTE including:
  - Pulmonary embolism and Pulmonary embolus.
  - Deep venous thrombosis.
- Cardiovascular events including:
  - Myocardial infarction, Acute myocardial infarction and Myocardial ischaemia.
  - Cerebrovascular accident, Transient ischaemic attack, Ischaemic stroke and Subarachnoid haemorrhage.
  - Peripheral occlusive disease.
  - Angina unstable and Angina pectoris terms
- Other thrombotic events

Number of VTE and CV events, n per 1000 patient-years (n/1000 PY) of exposure will be presented, which is defined as the summation of number of years for all the subjects at risk, calculated as:

$$\text{Events per 1000 Patient-Years} = n / PY * 1000$$

where,

n = number of events in each group.

PY = (End of Treatment Date – First treatment date + 1)/365.25 or

(cut-off date – First treatment date + 1)/365.25 for ongoing subjects.

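### The VTE and cardiovascular rates can count events up to the follow-up visit, while person-time stops at an undefined end-of-treatment date

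*SAP*

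**What the plan says.** SAP 7.7.1.1 (Adverse Events) asks for the incidence of VTE and cardiovascular events, and adds that "n per 1000 patient-years (n/1000 PY) of exposure will be presented". The numerator is defined only as "n = number of events in each group". The denominator is "PY = (End of Treatment Date – First treatment date + 1)/365.25", with the data cut-off date substituted for women still on treatment.

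The bullet belongs to a list whose lead-in names the events to be summarized: "All TEAEs (including AESI and SAE), SAE (including serious AESI" and so on. SAP Table 1 sets the treatment-emergent window. An event qualifies if it starts on or after first dose and before the last visit, where "last visit is defined as end of treatment, early discontinuation or follow up visit (for NH subjects". For non-hysterectomized women SAP 3.1 says this follow-up visit "is planned approximately 10 days after completion of the 14 days of P4 treatment", and that it also takes place after early discontinuation.

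Table 1 does not define the End of Treatment Date. The nearest defined variable is Treatment Stop Date: "The date of last dose of study drug".

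On classification, SAP 7.7.1.1 groups events by listed terms, and verbatim descriptions are coded with MedDRA. Protocol 10.5 (version 8.0, 21 June 2022) provides a Clinical Event Committee "who will adjudicate cardiovascular and thrombotic events in a consistent and unbiased manner throughout the course of the study". SAP 3.0 is dated 7 July 2022, but its Section 1 says it is based on Protocol 7.1. Neither the analysis text nor SAP Section 8 (changes from the protocol) mentions the committee.

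**The concern.** A rate per person-time needs the same window above and below the line. Here the numerator appears to run to the last visit and the denominator only to end of treatment. For a non-hysterectomized woman the days between are the P4 course and the short interval after it. E4 has stopped, yet an event on those days can enter a rate labelled as being per unit of exposure.

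General safety is the primary objective of this study part, and Protocol 5.4 names thromboembolism as a known risk of menopausal hormone therapy. The count may be small, so the rule that decides whether one event belongs in the table should be explicit. The same applies to the source of the classification, because adjudicated and coded results for the same event can differ.

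**Working it through.** **Plan's own figure.** The documents give no VTE or cardiovascular rate and no patient-year total, so there is none to reproduce. The one related planning figure does check: 400 × (1 − 0.50) = 200 completers, as in Protocol 8.1.

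**Inputs**
- About 200 hysterectomized and 200 non-hysterectomized women (SAP 3.1); 50% dropout at 12 months (Protocol 8.1).
- Gap from end of treatment to follow-up: nominally 14 + 10 = 24 days. From the windows in SAP Table 5 (Day 365–371 and Day 379–392), the minimum is 379 − 371 = 8 days and the maximum 392 − 365 = 27 days.
- Completers treated for 365 days.
- Mean dropout day: **assumed**, since the documents do not give it. Days 30, 91 and 182 are shown, plus a no-dropout case.
- Every non-hysterectomized woman attends follow-up: **assumed**, relaxed below.

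**Person-time as written**

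PY = 400 × (0.5 × 365 + 0.5 × dropout day) / 365.25. For dropout day 182: 400 × 273.5 / 365.25 = 299.5.

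**Omitted person-time**

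200 × gap / 365.25 = 4.4, 13.1 or 14.8 PY for gaps of 8, 24 or 27 days.

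**Inflation of the overall rate**

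For a fixed event count, the rate as written divided by the aligned rate, minus 1, equals omitted PY / PY as written.

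| Mean dropout day | PY as written | 8-day gap | 24-day gap | 27-day gap |
|---|---|---|---|---|
| 30 | 216.3 | 2.0% | 6.1% | 6.8% |
| 91 | 249.7 | 1.8% | 5.3% | 5.9% |
| 182 | 299.5 | 1.5% | 4.4% | 4.9% |
| No dropout | 399.7 | 1.1% | 3.3% | 3.7% |

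**Attendance.** If only completers attend follow-up, the omitted time halves. At 24 days it is 100 × 24 / 365.25 = 6.6 PY, which is 2.2% of 299.5 or 3.0% of 216.3.

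**Effect on event counts (dropout day 182, 24-day gap)**
- One event: 1000 / 299.5 = 3.34 per 1000 PY as written; 1000 / (299.5 + 13.1) = 3.20 aligned to the last visit.
- Two events, one of them in follow-up: 2000 / 299.5 = 6.68 as written; 2000 / 312.6 = 6.40 with both windows to the last visit; 1000 / 299.5 = 3.34 with both restricted to treatment.

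The denominator mismatch moves the rate by a few percent. Whether the follow-up event is counted moves it by a factor of two.

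**The case against.** The strongest reply is that the label settles the matter. Person-time to end of treatment is what a rate per exposure needs, the formula says only number of events, and a sensible programmer would count events on treatment. This has some force: the treatment-emergent window for the numerator is inferred from the list heading and Table 1, not stated in the formula. But nothing restricts the count to treatment. If the treatment-emergent definition did not apply either, the numerator would have no stated end. By contrast, SAP 7.7.1.2 does set a post-drug cut-off (30 days) for laboratory data.

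The second reply is that the effect is small, and that is correct. For one event in 299.5 PY the exact Poisson 95% interval is about 0.1 to 18.6 per 1000 PY, which dwarfs a shift from 3.34 to 3.20. The bias is upward, and the SAP also lists all adverse events with treatment-emergent flags.

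Three stronger readings are tempting but not supported:
- A reader might infer that the mismatch spoils a planned comparison between hysterectomy strata. The VTE and cardiovascular bullet asks for no such split, although neighbouring bullets do, and SAP 7.8 limits stratum tables to those named in their own sections.
- A reader might infer that the SAP disregards adjudication. It is silent on it and is written to the protocol version before the committee was added. Protocol 10.5 has the committee support the DSMB and does not say that its classifications drive the analysis.
- A reader might infer that adjudicated results are already on file. Neither document shows this.

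**Conclusion.** The point holds as a minor defect of definition. As written, and reading the numerator as treatment-emergent events, the rate can take in events from about 24 post-treatment days per non-hysterectomized woman (8 to 27 by the visit windows) without the matching person-time. The overall rate is inflated by roughly 1% to 7%. That range rests on assumed dropout timing and on follow-up attendance; the lowest combination considered (8-day gap, completers only, dropout day 182) gives 100 × 8 / 365.25 = 2.2 PY, or 0.7% of 299.5.

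The more consequential question is whether an off-treatment event belongs in a rate of exposure, because one event can halve or double the result when counts are low.

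For hysterectomized women events stop at the end-of-treatment or early-discontinuation visit. A gap arises for them only if the End of Treatment Date means last dose and the visit comes later, which Protocol 10.1.6.6 allows for early terminators.

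The classification issue is an omission to be filled, not a contradiction between protocol and SAP.

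**What to change.** In SAP 7.7.1.1 and Table 1:
1. Define the End of Treatment Date, for example as the existing Treatment Stop Date.
2. State the event window for the numerator and use the same window for person-time.
3. Present two rates side by side: on-treatment (events and person-time both to last dose), which fits the exposure label, and first dose to last visit, with person-time extended to the last visit.
4. State whether the table uses committee-adjudicated or MedDRA-coded events. Where adjudicated results are available, present both.

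Items 1 to 3 are a text and programming change using dose, event and visit dates that the trial already records. Item 4 costs a sentence in the SAP. Showing the adjudicated version also depends on the committee's results being available to the analysis, which the documents do not establish.

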**Table 4: Reproductive system and abdominal pain preferred terms**

	AEBODSYS	AEDECOD
Reproductive system	Reproductive system and breast disorders	

Abdominal pain	Gastrointestinal disorders	Abdominal pain Abdominal pain lower Abdominal pain upper
----------------	----------------------------	--

Listings will be provided for the Included Set (including flagged for TEAEs) include:

- AEs
- AEs leading to deaths
- All SAEs (including serious AESI)
- AEs leading to dose interruption and discontinuation
- All AESI (including serious and non-serious AESI)
- VTE in the cardiovascular and cerebrovascular system

#### 7.7.1.2 Clinical Laboratory Examinations

Routine clinical laboratory tests (hematology and chemistry) include:

- Hematology: hematocrit, hemoglobin, erythrocytes, platelets, leukocytes, neutrophils, lymphocytes, basophils, eosinophils and monocytes
- Chemistry: urea, creatinine, total bilirubin, alkaline phosphatase, alanine transaminase, aspartate transaminase, sodium, potassium, chloride, bicarbonate, calcium, albumin, total protein, lactate dehydrogenase (LDH), LDH isoenzymes (I, II, III, IV and V), troponin, and blood glucose

All laboratory data will be summarized in International System of Units (SI). Quantitative laboratory measurements reported as ' $< X$ ', i.e. below the lower limit of quantification (BLQ), or ' $> X$ ', i.e. above the upper limit of quantification (ULQ), will be converted to  $X$  for the purpose of quantitative summaries, but will be presented as recorded, i.e. as ' $< X$ ' or ' $> X$ ' in the listings. The summaries will include all laboratory assessments collected no later than 30 days after the last drug/exposure date.

Descriptive statistics of observed values and change from baseline (n, mean, SD, median, min, and max) for continuous assessments will be provided by visit for the Safety Analysis Set. In case of multiple measurement at the same visit, the last observed value will be summarized. This last observed value will include all visits regardless of scheduled or unscheduled.

Values outside the normal range will be categorized as high (above the normal range) or low (below the normal range) based on the reference range of the safety laboratories.

Shift tables will be used to summarize the change in frequency counts (n) and percentages of subjects with normal, high or low from baseline to post-dose scheduled visits for the Safety Analysis Set.

Listings will be provided for hematology and chemistry laboratory data for the Included Set.

A listing of urinary pregnancy tests performed will be also provided for the Included Set.

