Samples for clinical blood tests will be taken during the Screening Period, at Visit 1 (baseline) and at the EoT (Visit 7 Efficacy Study part/Visit 6 Safety Study part). Samples will be processed in the central laboratory for analysis of the following parameters:

- Hematology: hematocrit, hemoglobin, erythrocytes, platelets, leukocytes, neutrophils, lymphocytes, basophils, eosinophils and monocytes
- Chemistry: urea, creatinine, total bilirubin, alkaline phosphatase, ALT, AST, sodium, potassium, chloride, bicarbonate, calcium, albumin, total protein, lactate dehydrogenase (LDH), LDH isoenzymes (I, II, III, IV, V), troponin, and blood glucose
- A urinary pregnancy tests may be performed at the discretion of the Investigator during the Screening visit and during the Randomization/Treatment allocation visit (Visit 1)

A sample for lipid and glucose parameters will be taken at washout visit or at screening visit and will be processed in the central laboratory for analysis of the following parameters:

- Lipid parameters: triglycerides, HDL-cholesterol, LDL-cholesterol, total cholesterol

- Glucose parameters: fasting glucose, glycated hemoglobin

The results of the above mentioned hematology, chemistry, lipid and glucose parameters will be analyzed during the trial on an ongoing basis and will be reported during the trial to the Investigator for safety monitoring. After review of the laboratory data, the Investigator must sign and date each laboratory report.

The laboratory will provide normal reference ranges for the laboratory results, and the laboratory report will flag all abnormal values. The Investigator will assess the clinical relevance of values outside the normal range and repeat, if needed, any clinically significant abnormal laboratory test.

Laboratory results should only be recorded and reported as AEs if they are considered as clinically significant, i.e., if they are associated with clinical symptoms, require active management, constitute SAEs or lead to discontinuation of treatment. As far as possible, the clinically significant abnormal laboratory value, as such, should not be recorded on the eCRF pages as an AE; rather, the etiology of the abnormality should be identified, and any clinical signs, symptoms or diagnoses which correspond to the laboratory abnormality should be recorded as an AE (Section 10.4.1).

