## **2 STUDY OBJECTIVES AND ENDPOINTS**

### **2.1 Primary Objective and Endpoint**

To evaluate the general safety of treatment with Estetrol (E4) 20 mg.

Safety endpoints for primary objective #1

- Frequency of Treatment Emergent Adverse Event (TEAE) (including Serious Adverse Events [SAEs])
- Frequency of changes in results in physical and gynecological examinations, vital signs, electrocardiogram (ECG), mammography, and breast examination at each measured time point
- Frequency of changes in routine clinical laboratory tests results (hematology and chemistry) at each measured time point

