## 7 STATISTICAL METHODS

### 7.1 General Statistical Conventions

All statistical procedures will be completed using SAS version 9.4 or higher, there is only one treatment group, thus no formal statistical analysis will be performed.

Confidence intervals (CIs) will be presented as 2-sided 95% CIs unless specified differently in specific analysis.

Categorical variables will be summarized using frequency counts (n) and percentages in each category, percentages will be computed for subjects with non-missing value (as the denominator). If there are missing values, missing values counts will be provided. All percentages will be rounded to one digit after decimal point. The frequency counts and percentages will be presented in the form XX (XX.X %), where the percentage is in the parentheses. If the percentage of a category is '100 %', then it will be displayed as '100 %' (no decimals will be added after 100).

Continuous variables will be summarized using the number of subjects with non-missing values (n), mean, median, standard deviation (SD), minimum (min), maximum (max) and missing values counts. Missing values counts will be displayed only if there are missing values. All mean and median values will be formatted to one more decimal place than the measured value. Standard deviations will be formatted to two more decimal places than the measured value. The min and max will be displayed to the same number of decimal places as the measured value. Unscheduled visits will not be summarized in tables.

Analyses will be performed by visit, irrespective of any time window deviations, unless otherwise specified. The early discontinuation (ED) visit will be separated from the scheduled EoT- visit based on discontinuation reason. Unscheduled visits related to efficacy data will be clustered with scheduled visits based on the visit windows in [Table 5](#) of Appendix 1. Similarly, the unscheduled visit results will be clustered with scheduled visits based on the visit windows defined in [Table 6](#) (Appendix 1) for microscopic findings and laboratory endpoints and endometrial biopsy. Similarly, the scheduled visits for ECG, Procedures, Questionnaire, Vital Signs, Imaging and Findings will be based on visit window [Table 7](#) in Appendix 1.

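### Laboratory by-visit summaries keep the last value at a visit, so in women who complete treatment a normal off-drug repeat can replace an abnormal end-of-treatment result

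*SAP*

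**What the plan says.** One primary endpoint of the Safety Study part is: "Frequency of changes in routine clinical laboratory tests results (hematology and chemistry) at each measured time point" (SAP 2.1). Protocol 10.4.5 sets the sampling: "Samples for clinical blood tests will be taken during the Screening Period, at Visit 1 (baseline) and at the EoT". EoT is therefore the only scheduled post-baseline sample. The same section asks the investigator to "repeat, if needed, any clinically significant abnormal laboratory test".

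SAP 7.7.1.2 sets three rules for these data:
- **Time limit:** "The summaries will include all laboratory assessments collected no later than 30 days after the last drug/exposure date".
- **Value kept**, in the paragraph on descriptive statistics for continuous assessments: "In case of multiple measurement at the same visit, the last observed value will be summarized". The next sentence adds: "This last observed value will include all visits regardless of scheduled or unscheduled".
- **Shift table**, in a separate paragraph: it counts women as "normal, high or low from baseline to post-dose scheduled visits for the Safety Analysis Set". No rule there says which value to use when a visit has several.

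SAP 7.1 states that "the unscheduled visit results will be clustered with scheduled visits based on the visit windows defined in" Table 6, and SAP 7.7 applies the Table 6 and 7 clustering to all safety endpoints. SAP 7.1 also says that tables leave unscheduled visits out.

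**The concern.** In completers, any sample after the EoT visit is off drug. The protocol prompts a repeat when a result is abnormal and clinically significant, and does not call for repeating a normal one. A rule that keeps the latest value therefore works mainly one way: an abnormal EoT result can give way to a normal repeat, with no matching process that turns normal results abnormal.

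With a single scheduled post-baseline sample, no other planned laboratory summary would show the lost value. No worst-value laboratory table is planned, although SAP 7.7.1.12.2 plans a worst-case on-treatment analysis for biopsies. In a single open-label arm there is also no control group to show how much the rule changes the picture. At stake is whether the Week 53 statistics, and possibly the shift table, describe women at the end of exposure or after it.

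**Working it through.** The plan states no figure for this point, so there is none to reproduce. The check applies the SAP windows by day arithmetic.

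**Inputs**
- EoT visit (Visit 6): Day 365 to 371 (Protocol Table 4).
- Last dose: the evening before EoT (Protocol 10.1.6.6), so Day 364 to 370.
- Limit for laboratory summaries: 30 days after last drug (SAP 7.7.1.2).
- Week 53 window for unscheduled samples (SAP Table 6): Day 327 onward with no upper bound for hysterectomized women; Day 326 to 375 for non-hysterectomized women, with Day 376 onward going to Follow-up.
- Early discontinuers' Visit 6 sample: its own Early Discontinuation row (SAP Table 6).
- Expected dropout in the Safety part: 50% of about 400 (Protocol 8.1), so 400 × (1 − 0.50) = 200 completers, as the protocol states.

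**How late a repeat can replace the EoT value in completers**

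| | EoT Day 365 | EoT Day 371 |
|---|---|---|
| Last dose | Day 364 | Day 370 |
| 30-day limit | 364 + 30 = Day 394 | 370 + 30 = Day 400 |
| Hysterectomized: days after EoT | 394 − 365 = 29 | 400 − 371 = 29 |
| Non-hysterectomized: days after EoT | 375 − 365 = 10 | 375 − 371 = 4 |
| Non-hysterectomized: days off drug | 375 − 364 = 11 | 375 − 370 = 5 |

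The full 30-day reach applies only to hysterectomized completers. For non-hysterectomized completers it is 4 to 10 days after EoT.

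**Early discontinuers.** Take a discontinuation visit on Day 200 and a repeat on Day 214. The first sample goes to the Early Discontinuation row. The repeat falls in Day 145 to 242 and is shown as Week 29. With a visit on Day 100 and a repeat on Day 114, the repeat falls in Day 75 to 144 and is shown as Week 13. The abnormal value is not overwritten, because it has its own row and hematology and chemistry have no scheduled sample at those weeks. An off-drug value does appear under an on-treatment label.

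**Does the rule reach the shift table?**
- *For:* SAP 7.7 clusters visits for all safety endpoints, a shift table needs one value per woman per visit, and the last-value rule is the section's only selection rule.
- *Against:* the rule sits in the continuous-statistics paragraph, the shift table is described by scheduled visits, and SAP 7.1 leaves unscheduled visits out of tables.

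The extension is plausible but contradicted.

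**Size.** Among completers, the share of out-of-range EoT values lost is c × r × s. Here c is the share judged clinically significant, r the share of those repeated inside the window, and s the share that normalise. The documents give none of the three. Purely as an illustration, assume c = 0.05 to 0.20 and r and s each 0.3 to 0.7:
- low: 0.05 × 0.3 × 0.3 = 0.0045, or 0.45%;
- high: 0.20 × 0.7 × 0.7 = 0.098, or 9.8%.

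If 10% of 200 completers (20 women) were out of range on some parameter, that is 20 × 0.0045 = 0.09 to 20 × 0.098 = 1.96 women.

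**The case against.** The strongest reply is that no effect on the primary endpoint has been shown. That endpoint is a frequency of changes, which the shift table carries, and the last-value sentences belong to the continuous statistics. This stands to the extent that the SAP does not state the extension. It does not settle the matter, because the clustering text points the other way and no alternative selection rule is given.

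A second reply is that nothing is lost to the reader of the report. All results, including unscheduled ones, stay in the listings, and clinically significant results are reportable as adverse events. It is true that the data do not disappear. The backstop is incomplete, however: listings give no frequency, and Protocol 10.4.5 prefers the underlying diagnosis to the laboratory value as the reported event.

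A third reply is that the analysis is descriptive, with one arm and no formal test, so no inferential decision turns on it. That limits the consequence but does not justify a summary rule that leans one way.

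A reader might also infer that 9% to 49% of abnormal results vanish, from r × s alone with r and s between 0.3 and 0.7. That sets c = 1, as if every out-of-range value were clinically significant and eligible for a prompted repeat. The protocol prompts repeats only of clinically significant results, and only if needed, while the shift table counts any value outside the reference range. The documents do not support that range.

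**Conclusion.** The point holds for completers' by-visit statistics. As written, the SAP lets a normal off-drug repeat replace an abnormal value from the only scheduled post-baseline sample, which affects the mean and can lower the reported maximum. The repeat can come up to 29 days after EoT in hysterectomized women and 4 to 10 days after in non-hysterectomized women. The direction follows from the protocol's repeat rule. The size depends wholly on c, r and s, which are not given, and may be small.

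Three stronger readings are not supported. It is not established that abnormal results are removed from the primary endpoint's shift table; the text is contradictory and needs reconciling. The 30-day reach does not apply to all women. Early discontinuers, about half the arm by the protocol's expectation, do not have their abnormal value overwritten; their problem is a repeat labelled with the wrong treatment period. This is worth correcting before database lock.

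**What to change.** - Use the scheduled EoT or early-discontinuation sample for both the by-visit statistics and the shift tables. Use an unscheduled value only when the scheduled one is missing.
- Add a shift table from baseline to the worst value from first dose through the EoT or early-discontinuation sample. Do not end this window at last dose plus one day: Protocol 10.1.6.6 recognises that treatment may have stopped before an early-termination visit, so that cut-off could drop a woman's only post-baseline sample. With one scheduled sample the table will largely match the scheduled shift table; what it adds is any unscheduled abnormal value found earlier.
- Present later off-drug repeats separately or in listings, and do not window them into on-treatment weeks.
- Reconcile SAP 7.1, SAP 7.7.1.2 and Table 6, and state which value feeds the shift table.

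The cost is a short SAP edit and one extra table, with no new data. Abnormality rates may look slightly less favourable.
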